#### Interim Analysis

For each dose level expanded, an interim analysis of efficacy will be performed after 16 patients have been dosed. If one or fewer patients have a BOR of CR or PR (not necessarily confirmed 4 weeks later) accrual to this cohort will be stopped.

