#### Phase 1 Dose Expansion Footnotes

- 1 ECOG performance scale is available in Appendix 1.
- 2 Vital signs (VS) include blood pressure (BP), temperature (T), and heart rate (HR). See Table 5 for collection time points.
- 3 Height is required at screening only.
- 4 A full physical exam is required at screening only. All other physical exams may be symptom directed.
- 5 Lab Assessments should include:
  - Hematology labs: CBC with Differential
  - Chemistry labs: Na, K, Cl, CO2, BUN, Cr, glucose, Ca, total bili, AST, ALT, ALP, albumin, total protein, Mg
  - Urinalysis: pH, specific gravity, glucose, ketones, blood, protein, nitrates, leukocytes
  - Coagulation: PT, PTT, INR
  - Pregnancy labs can be performed via blood or urine
  - Plasma EBV DNA
- 6 Pregnancy tests on D1 of each cycle and at the Safety FU visit are only required at sites in the EU. For sites in other regions, pregnancy tests at these visits are only required if clinically indicated.
- 7 All ECGs must be performed in triplicate. See Table 5 for specific collection time points.
- 8 VK-2019 must be taken in the morning on an empty stomach. Patients must fast for one hour before and two hours after each dose. Study drug accountability will be performed at each visit.
- 9 See Table 5 for PK collection time points. PK samples will only be collected through C3D0, not beyond.
- 10 Assessments need not be repeated if performed within three days prior to the visit.
- 11 Tumor assessments must be performed using computed tomography (CT), positron emission tomography (PET)/CT, or magnetic resonance imaging (MRI). Assessments should include evaluation of the neck, chest, abdomen, and pelvis, Post-baseline assessments will be performed within seven days of D0 of odd numbered cycles (i.e., C3D0, C5D0, etc).
- 12 Tumor assessments performed within four weeks of the EOT visit need not be repeated.
- 13 Tumor assessments in LTFU are only required for patients that have discontinued for reasons other than radiographic progression of disease, and may be performed  $\pm 2$  weeks of the scheduled LTFU date.
- 14 Survival status may be assessed via clinic visit (either at the study site or outside facility), telephone, or videotelephony.

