## Sample Size Determination

The number of patients in the dose escalation phase is estimated to be 30 patients (assuming six patients will be dosed in each of five cohorts). The number of patients in the Phase 1 Dose Expansion and Phase 2a Dose Expansion is based on a Simon 2-stage design as described below. The approximate sample size in the Phase 1 Dose Expansion is estimated to be 20 patients (assuming 10 additional patients in each of two expanded dose levels). During the Phase 2a portion of the trial, the approximate sample size in the Phase 2a Dose Expansions is estimated to be 18 (assuming 9 patients in each of two expansion cohorts). In total, it is estimated that up to approximately 68 patients will be dosed in this trial.

The number of patients for the Phase 1 and 2a expansions is based upon a Simon Two-Stage design at BCAD and MTD, respectively. The null hypothesis that the true response rate is 0.1 will be tested against a one-sided alternative. In the first stage (i.e., a Phase 1 Dose Expansion cohort), a total of 16 patients will be accrued. If there is one or fewer responses in these 16 patients, accrual to this cohort will be stopped. Otherwise, 9 additional patients will be accrued (i.e., a Phase 2a Dose Expansion cohort) for a total of 25. The null hypothesis will be rejected if five or more responses are observed in 25 patients. This design yields a 1-sided type I error rate of 10% and power of 90% when the true response rate is 30%. This design yields a probability of 0.51 for a cohort stopping early if the true response rate for that cohort is 10%. The sample size in the dose escalation phase is not based on statistical considerations, but rather depends on the number of observed toxicities; up to 6 subjects are expected to be treated after the accelerated titration design has ended at each conventional escalation cohort dose prior to the expansion cohort at MTD.

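### The first-stage futility rule is timed by dosing of the 16th patient and does not require the 16 to have been scanned, so it can be read before 16 outcomes are known

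*Protocol*

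**What the plan says.** The timing is in the Protocol, Interim Analysis (Section 14.10): "For each dose level expanded, an interim analysis of efficacy will be performed after 16 patients have been dosed". The rule follows directly: "If one or fewer patients have a BOR of CR or PR (not necessarily confirmed 4 weeks later) accrual to this cohort will be stopped". No minimum follow-up, scan requirement or handling of patients without a scan is given.

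Sample Size Determination (Section 14.3; repeated in the Synopsis and in SAP Section 5) fixes the first-stage denominator: "If there is one or fewer responses in these 16 patients, accrual to this cohort will be stopped". For the final analysis, "The null hypothesis will be rejected if five or more responses are observed in 25 patients". The stated properties are one-sided type I error 10%, power 90% at a true rate of 30%, and a 0.51 chance of early stopping at a true rate of 10%.

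On scans, the Phase 1 Dose Expansion footnotes say: "Post-baseline assessments will be performed within seven days of D0 of odd numbered cycles (i.e., C3D0, C5D0, etc"). Cycles last 28 days.

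Three other places bear on the point:
- Section 6.1.2 lets the SRC put off its decision pending more data, and leaves the timing of its reviews to the SRC Charter.
- Initiation of Phase 2a Expansion Cohorts (Section 6.8) requires a completed Phase 1 expansion cohort and at least two responders, one of them confirmed. It sets no time limit.
- SAP Section 7.15 gives no interim method; it says only that no output will be produced for the abbreviated report.

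**The concern.** A two-stage design has its stated error rates only if the first-stage count is taken over the full first-stage sample. Here the trigger is an enrolment event, while the outcome it needs normally appears no earlier than about 8 weeks later. A patient dosed in the 8 weeks before the look can add nothing to the response count, yet the bound of one stays where it was set for 16 outcomes.

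The definition of a completed cohort does not close the gap. The only one given (Section 6.2.1) is for escalation cohorts and rests on Cycle 1 dosing or a DLT, not on a scan. The Response Evaluable population does not close it either. It leaves out a patient who is still on treatment and unscanned, but the bound is not rescaled to the smaller number, so the effect on stopping is the same.

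This rule governs whether a dose goes on to Phase 2a. An early reading can close accrual at a dose that would have passed had all 16 outcomes been known.

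**Working it through.** **Inputs from the documents.** Null rate 0.10 and target rate 0.30; first stage 16 patients, stop at one response or fewer; total 25, reject at five or more (Section 14.3). First scan at C3D0 = 2 × 28 = 56 days after first dose, window ± 7 days.

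**Input assumed.** Accrual per dose level is not given. I take 1, 2 or 3 patients per 28 days, evenly spaced.

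**Formulas.** Let m be the number of the 16 who have been scanned at the look, and p the true response rate.
- Stop probability: (1−p)^m + m·p·(1−p)^(m−1).
- Rejection probability: the sum over x = 2 to m of P(X = x)·P(Y ≥ 5−x), with X ~ Bin(m, p) and Y ~ Bin(25−m, p). Unscanned patients add nothing at the look but count in full at the end if the cohort continues.

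**Step 1: reproduce the plan (m = 16).**
- Stop at p = 0.10: 0.9^16 + 16 × 0.1 × 0.9^15 = 0.1853 + 0.3294 = 0.515 (plan: 0.51).
- Stop at p = 0.30: 0.7^16 + 16 × 0.3 × 0.7^15 = 0.0033 + 0.0228 = 0.026.
- Rejection probability: 0.095 at p = 0.10 (plan: 10%) and 0.903 at p = 0.30 (plan: 90%).

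The plan's figures are right when all 16 outcomes are known.

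**Step 2: how many are unscanned when the 16th is dosed.** Patients dosed within the last 56 days number 56/28 × rate: 2, 4 or 6 at 1, 2 or 3 per 28 days.

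**Step 3: apply the unchanged bound to m scanned patients.**

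| Scanned (unscanned) | Assumed accrual per 28 days | Stop, p = 0.30 | Power, p = 0.30 | Stop, p = 0.10 | Type I error |
|---|---|---|---|---|---|
| 16 (0) | all assessed | 0.026 | 0.903 | 0.515 | 0.095 |
| 14 (2) | 1 | 0.047 | 0.891 | 0.585 | 0.091 |
| 12 (4) | 2 | 0.085 | 0.864 | 0.659 | 0.083 |
| 10 (6) | 3 | 0.149 | 0.811 | 0.736 | 0.072 |

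For example, with m = 12 and p = 0.30: 0.7^12 + 12 × 0.3 × 0.7^11 = 0.0138 + 0.0712 = 0.085.

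**Step 4: sensitivity to the scan window.** If the first scan falls at day 63, one more patient is unscanned in each row (3, 5 or 7), and power is 0.880, 0.841 or 0.770. At day 49 the numbers unscanned are those in the table.

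**Direction.** Type I error falls and the stop probability rises in every row, so the error is one-sided. The calculation treats a scanned patient's status as final. Responses first seen at C5D0 (day 112) would add to the loss.

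**The case against.** The best defence is that the trigger sets an earliest time, not a data cut on the day the 16th patient is dosed. The rule is written in terms of best overall response, which needs a scan, and Section 14.3 speaks of responses among the 16. An interim held after all 16 have been scanned would comply. This stands: a premature reading is permitted, not compelled.

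Second, the stop need not be final. Phase 1 enrolment at a dose is capped at 16, so accrual pauses there whatever the interim shows. Going further is a separate SRC decision that may be deferred, and the Phase 2a gate has no clock. Patients already dosed continue to be scanned. The SRC Charter, which is not among the documents, may also contain a timing rule. This softens the point but does not remove it, because Section 14.10 words the stop as mandatory and nothing says which text prevails.

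Third, the size is uncertain. At 1 patient per 28 days the power loss is about one point. Escalation patients count within the 16 and will usually have been scanned already; on the planning figure of 10 additional patients per expanded dose, at most about 10 could be unscanned. Section 14 also disclaims confirmatory inference. All of this limits the severity.

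A reader might infer that unscanned patients are to be scored as non-responders. No sentence says so; it is only what a fixed count does in effect if read early. A reader might also infer that an early stop means the Phase 2a question at that dose is never addressed. Sections 6.1.2 and 6.8 do not support that.

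**Conclusion.** The stated 10%, 90% and 0.51 are correct for 16 assessed patients, but the trigger does not impose that condition. The defect is a decision rule that permits a reading under which its own operating characteristics fail, always towards stopping.

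Under the assumed accrual, power at a true 30% rate falls by about 1 point (0.903 to 0.891), 4 points (to 0.864) or 9 points (to 0.811). The chance of wrongly stopping is up to about six times the designed value (0.149 against 0.026). These figures assume evenly spaced entry, a look taken as soon as the 16th patient is dosed, and no waiting by the SRC. It would be too strong to say that the plan as written fails to deliver 90% power: that depends on when the look is taken and on an accrual rate the documents do not give. The point should be fixed, but it does not invalidate the design.

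**What to change.** In Section 14.10, replace the dosing trigger: perform the interim once each of the 16 patients at that dose level has had the C3D0 tumour assessment, or has progressed, died or discontinued before it.

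Then settle late responses by choosing one of two statements. Either a cohort at or below the bound is not closed while an unconfirmed or pending assessment among the 16 could still change the count, or responses first seen at C5D0 are not awaited. The C3D0 trigger alone does not decide this.

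Repeat the trigger in the Synopsis sample-size text, Section 14.3, and SAP Sections 5 and 7.15. Reconcile it with Section 6.8: define completion of a Phase 1 expansion cohort, and say how the unconfirmed count at the interim relates to the requirement for one confirmed response. Confirmation needs a second scan at least 4 weeks later, and the next scheduled scan after C3D0 is C5D0, so the C3D0 trigger cannot simply be carried over to that section. Say also whether the SRC's option to defer overrides the mandatory stop.

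The cost is a wait of about 8 weeks (up to 9 with the scan window) after the 16th patient is dosed, and longer if C5D0 scans are awaited. No additional patients or scans are needed.

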# **15 STUDY MANAGEMENT**

#### Pre-study Documentation

This study will be conducted in accordance with the ethical principles that have their origin in the Declaration of Helsinki as stated in 21 CFR §312.120(c)(4); consistent with GCP and all applicable regulatory requirements.

Before initiating this trial, the Investigators will have written and dated approval from the Institutional Review Boards for the protocol, written informed consent form, subject recruitment materials, and any other written information to be provided to subjects before any protocol related procedures are performed on any subjects.

The clinical investigation will not begin until either FDA has determined that the study under the IND is allowed to proceed.

The Investigator must comply with the applicable regulations in Title 21 of the Code of Federal Regulations (21 CFR §50, §54, and §312), GCP/ICH guidelines, and all applicable regulatory requirements. The IRB must comply with the regulations in 21 CFR §56 and applicable regulatory regulatory requirements.

#### **Informed Consent**

All participants must be provided a consent form describing the study with sufficient information for each participant to make an informed decision regarding their participation. Participants must sign the IRB/IEC-approved informed consent form prior to participation in any study specific procedure. The participant must receive a copy of the signed and dated consent document. Documentation of participant signature may be made by facsimile copy or other electronic transmission such as electronic photograph of signed consent document. A high-resolution scan or photograph of a signed consent is considered adequate documentation. The original signed copy of the consent (or scanned/ photographic copy thereof) document must be retained in the medical record or research file.

## **Changes in the Protocol**

Once the protocol has been approved by the IRB/IEC, any changes to the protocol must be documented in the form of an amendment. The amendment must be approved by each site's IRB/IEC prior to implementation at that site.

If it becomes necessary to alter the protocol to eliminate an immediate hazard to patients, an amendment may be implemented prior to IRB/IEC approval. In this circumstance, however, the Investigator must then notify the IRB/IEC at each site in writing within five (5) working days after implementation. The study sponsor and the study team will be responsible for updating any participating sites.

## Handling and Documentation of Clinical Supplies

The Principal Investigator and each participating site will maintain complete records showing the receipt, dispensation, return, or other disposition of all investigational drugs. The date, quantity and batch or code number of the drug, and the identification of patients to whom study drug has been dispensed by patient number and initials will be included.

The Investigators shall not make the investigational drug available to any individuals other than to qualified study patients. Furthermore, the investigators will not allow the investigational drug to be used in any manner other than that specified in this protocol.

# Case Report Forms (CRFs)

The Principal Investigator at each site and/or his/her designee, will prepare and maintain adequate and accurate participant case histories with observations and data pertinent to the study. Study specific Case Report Forms (CRFs) will document safety and treatment outcomes for safety monitoring and data analysis. All study data will be entered into the clinical trial database via standardized CRFs (paper or secure electronic) in accordance with the study calendar. The investigator's designee at each site will complete the CRFs as soon as possible upon completion of the study visit.

The information collected on CRFs shall be consistent with the original source documents. Source documents will be found in the patient's medical records maintained by site personnel. In accordance with federal regulations, the Investigator is responsible for the accuracy and authenticity of all clinical and laboratory data entered onto CRFs at their site. Each site PI will approve all completed CRFs to attest that the information contained on the CRFs is true and accurate.

All source documentation and data will be available for review/monitoring by the sponsor and regulatory agencies. A high-resolution scan or photograph of signed CRFs is considered adequate documentation and the official EMR is considered adequate primary source documentation. Not all EMR source documentation need be reproduced within separate clinical trials study materials in paper form. Storage of locked PDF documents is an acceptable alternative to paper copies of protocol related documents, including consent forms and data from the EMR.

The Principal Investigator will be responsible for ensuring the accurate capture of study data. At study completion, when the CRFs have been declared to be complete and accurate, the database will be locked. Any changes to the data entered into the CRFs after that time can only be made by joint written agreement among the PI, the Trial Statistician, and the Sponsor.

## **Study Monitoring**

During the course of the trial, a monitor appointed by the Sponsor will make site visits to review protocol compliance, compare CRFs and individual patient's medical records, assess drug accountability, and ensure that the trial is being conducted according to pertinent regulatory requirements. CRF entries will be verified with source documentation. The review of medical records will be performed in a manner to ensure that patient confidentiality is maintained.

## Inspection and Retention of Records

Cullinan Apollo or a Cullinan Apollo representative, a regulatory authority, an IRB or IEC may visit the clinical site to perform audits or inspections, including source data verification. The purpose of an audit or inspection is to systematically and independently examine all study-related activities and documents to determine whether these activities were conducted, and data were recorded, analyzed, and accurately reported according to the protocol, Good Clinical Practice guidelines of the International Conference on Harmonization, and any applicable regulatory requirements. Direct access to source data will be required for these audits and inspections; they will be carried out giving due consideration to data protection and medical confidentiality. The PI

or designee is responsible for providing necessary support at all times. The PI or designee should contact Cullinan or designee immediately if contacted by a regulatory agency about an inspection.

According to ICH guidelines, the PI must maintain all documentation relating to the study for a period of 2 years after the last marketing application approval and until there are no pending or contemplated marketing applications in an ICH region or for at least 2 years following the discontinuation of clinical development of the investigational product. These documents should be retained for a longer period if required by applicable legal requirements.

# Quality Control and Quality Assurance

The Sponsor or designee will conduct a site visit to verify the qualifications of each PI and designee, inspect the site facilities, and inform the PI of responsibilities and the procedures for ensuring adequate and correct documentation.

The CRFs for each patient will be checked against source documents at the clinical site by the monitor (Source Data Verification [SDV]).

In the case of electronic CRFs, the site monitor can also review CRFs remotely at any time during the trial and generate queries for site resolution prior to the site monitoring visit.

Instances of missing or uninterpretable data will be queried by the site monitor for site resolution.

The data management plan, to be developed during the initiation of the trial, will include specifications for consistency and plausibility checks on data. CRF completion guidelines will also be developed and include data entry instructions for the site. Queries raised during data management review of SDV data will be generated for site resolution with the PI or designee. The site will either update the CRF if original data is incorrect or will provide a confirmation that the data is correct. Data Management can also review data and generate queries prior to SDV to expedite data clean-up. The site can then update the CRF if needed and the site monitor will verify the update during SDV.

# **17 APPENDICES**

[figure not shown]
# Appendix 1 - Performance Status Criteria

ECOG Performance Status Scale		Karnofsky Performance Scale	
Grade	Descriptions	Percent	Description
0	Normal activity Fully active, able to carry on all pre-disease performance without restriction	100	Normal, no complaints, no evidence of disease
		90	Able to carry on normal activity; minor signs or symptoms of disease
1	Symptoms, but ambulatory Restricted in physically strenuous activity, but ambulatory and able to carry out work of a light or sedentary nature ( e.g. , light housework, office work)	80	Normal activity with effort; some signs or symptoms of disease
		70	Cares for self, unable to carry on normal activity or to do active work
2	In bed < 50% of the time Ambulatory and capable of all self-care, but unable to carry out any work activities Up and about more than 50% of waking hours	60	Requires occasional assistance, but is able to care for most of his/her needs
		50	Requires considerable assistance and frequent medical care
3	In bed > 50% of the time Capable of only limited self-care, confined to bed or chair more than 50% of waking hours	40	Disabled, requires special care and assistance
		30	Severely disabled, hospitalization indicated Death not imminent
4	100% bedridden Completely disabled	20	Very sick, hospitalization indicated Death not imminent
	Cannot carry on any self-care Totally confined to bed or chair	10	Moribund, fatal processes progressing rapidly
5	Dead	0	Dead

Aosetron:	lotronex
Bosentan:	Tracleer
Candesartan:	Atacand
Celecoxib:	Celebrex
Diclofnac:	Volaren
Dronabinol:	Marinol
Flubiprofen:	Ansaid
Fluvastatin:	Lescol
Glimepiride:	Amaryl
Ibuprofen:	Advil, Motrin
Indomethacin:	Indocin
Irbesartan:	Avapro
Losartan:	Cozaar
Meloxicam:	Mobic
Montelukast:	Singulair
Naproxen:	Aleve
Nateglinide:	Starlix Phenobarbital
Phenytoin:	Dilantin
Piroxicam:	Feldene
Rosiglitazone:	Avandia
Rosuvastatin:	Crestor Sulfmethoxazole Tolbutamide
Torsemide:	Demadex
Valsartan:	Diovan
Warfarin:	Coumadin

# Appendix 2 - Prohibited Medications During Treatment Cycle 1 and 2

NOTE: This list contains common drugs and is not all-inclusive. The study team should check a frequently-updated medical reference for a list of drugs to avoid or minimize use of OATP1B3 substrate prohibited medications.

